6.1 Disposition

The counts of patients who were screened will be presented. The counts and percentages of patients who are screen failures, randomized, and included in each analysis set will be presented.

Patients who completed or discontinued from the treatment period and study will be presented based on the number of patients who were randomized in each treatment group and entered in each treatment period along with both treatment groups pooled. Reasons for discontinuation for each treatment period or from the study will be summarized separately by treatment group for each treatment period. In addition, whether patients discontinued from the treatment period or study due to COVID-19 will also be summarized separately by treatment group for each treatment period.

6.2 Protocol Deviations

Patients with any major protocol deviations will be tabulated for each treatment group by deviation category (Consent/Accent; Procedures/Documentation; Eligibility; Study Medication Dispensing/Dosing; Other Medication Dosing; Prohibited Action; Serious Adverse Event

Reporting; Visit /Assessment Schedule) and treatment period for ITT analysis set. All major and minor protocol deviations observed in the trial will be listed by-patient for all patients enrolled.

7. Demographics and Baseline Characteristics

Demographics and baseline characteristics collected at Screening will be summarized for the ITT analysis set, mITT analysis set, and safety analysis set for the double-masked treatment period, and ITT analysis set for the open-label treatment period. If mITT and safety analysis sets are the same as the ITT analysis set, then summaries based on mITT and safety analysis sets will not be presented. Continuous variables (i.e., age [in years], baseline weight [kg], baseline height [cm], baseline body mass index [BMI in kg/m²], and time since diagnosis of TED [in years]) will be summarized by treatment group and overall using descriptive statistics. For the similar summary of the open-label treatment period, TEPEZZA Baseline will be used to summarize the baseline weight, baseline height and baseline BMI, and time since diagnosis of TED. The following categorical variables will be summarized by reporting the number and percentage of patients in each category for each treatment group and overall.

- Age category (<65, ≥65 years old)
- Sex (Male, Female)
- Study eye (right, left)
- Childbearing potential (Yes, No or N/A)
- Ethnicity (Hispanic or Latino, Not Hispanic or Latino)
- Race (White, Black or African American, Asian, American Indian or Alaska Native, Native Hawaiian or Other Pacific Islander, and Other)
- Tobacco Use (Former, Current, Never)
- Alcohol Use (Former, Current, Never)

Individual patient's demographics and baseline characteristics will be presented in a by-subject listing for all patients enrolled in the trial.

Ocular baseline characteristics will be summarized for the ITT analysis set, mITT analysis set, and safety analysis set during the double-masked treatment period and for the ITT analysis set during the open-label treatment period, on the study eye and fellow eye, separately. If mITT and safety analysis sets are the same as the ITT analysis set, then summaries based on mITT and safety analysis sets will not be presented. For the open-label treatment period, baseline values will be recalculated based on the TEPEZZA Baseline. Continuous variables for patient ocular baseline characteristics are proptosis (measured as proptosis evaluation of the Clinical Measures of Severity using a Hertel instrument provided by the Sponsor for consistency in measurement), **CCI** [REDACTED] and clinical activity score (CAS). These continuous

variables will be summarized using descriptive statistics for each treatment group and overall. Categorical variables such as binocular diplopia (measured as part of the Clinical Measures of Severity) and best corrected visual acuity (BCVA) (Normal/Mild/Moderate Low Vision/Severe Low Vision/ Blindness) will be summarized by treatment group and overall for each category.

7.1 Substance Use

The data of substance use will be presented in a by-subject listing for all patients enrolled in the trial.

7.2 Medical History

General medical history will be summarized by system and organ class (SOC) and preferred term (PT) coded according to Medical Dictionary for Regulatory Activities (MedDRA) version 24.0.

The medical history data for all patients enrolled in the trial will be presented in a by-subject listing.

7.3 Inclusion and Exclusion Criteria

Inclusion and exclusion criteria deviations noted in the electronic case report form (eCRF) will be presented for all patients who provide informed consent in a by-subject listing. If there are patients who were enrolled in the trial despite they did not meet at least 1 of the entry eligibility criteria, the eligibility criterion or criteria that patients did not meet will be summarized by treatment group.

8. Treatments and Medications

8.1 Prior and Concomitant Medications

The concomitant medications will be summarized based on the eCRF collected information for all medications that patients have taken before or during the course of the clinical trial.

Prior medications are defined as all medications which start before the first dose of study drug. Concomitant medications during the double-masked treatment period are defined as all medications that start on or after the first dose of study drug until 21 days following the last dose of study drug or medications that start before the first dose of study drug and continue during the double-masked treatment period. Medications that start before the first dose of study drug and continue during the double-masked treatment period will be counted as both prior and concomitant medications. Concomitant medications during the open-label treatment period are defined as all medications that start on or after the first dose of TEPEZZA until 21 days following the last dose of TEPEZZA in the open-label treatment period, or medications that start before the first dose of TEPEZZA in the open-label treatment period and continue during the open-label treatment period. Medications that start in the double-masked treatment period and continue in the open-label treatment period will be counted as concomitant medications for both double-masked treatment period and open-label treatment period. Concomitant medications

during the follow-up period are defined as all medications that start after 21 days of the last dose of study drug through completion of follow-up period, or medications that start before 21 days of the last dose of study drug and continue during the follow-up period.

All medications will be mapped to the preferred terms according to WHODrug dictionary version March 2021.

The number and percentage of patients in each treatment group using prior medications and concomitant medications will be summarized by Anatomical Therapeutic Chemical (ATC) Level 4 term and Preferred Term. At each level of report, a patient will be counted only once even if the patient has taken more than one medication in the level.

All prior and concomitant medications (including concomitant medications during the follow-up period) will be presented in a by-subject listing with an indicator to identify whether their use is prior and /or concomitant.

8.2 Concomitant Procedures

All concomitant procedures performed during the trial will be presented in a by-subject listing for all patients enrolled.

8.3 Restricted Medications and Surgical Procedures

The restricted medications and surgical procedures are specified in Table 9.1 in protocol.

- Restricted surgical procedures are (1 category):
 - “orbital irradiation, orbital decompression or strabismus surgery”. This category will be captured via medical history eCRF form.
- Restricted medications or drugs are (9 categories):
 - “steroids”, “Rituximab (Rituxan® or MabThera®)”, “Tocilizumab (Actemra® or Roactemra®)”, “TEPEZZA”, “monoclonal antibody”, “non-steroid immunosuppressive agent (other than rituximab or tocilizumab)”, “investigational agent” and “Neonatal Fc receptor (FcRn) agents”. These categories will be captured via concomitant medications eCRF form.
 - “illicit drug/alcohol abuse”: This category will be captured via medical history and adverse event eCRF forms.

All restricted medication categories described above are reviewed manually by Horizon patient safety and pharmacovigilance.

The number and percentage of patients who received restricted surgical procedures in each treatment group will be summarized by SOC and preferred terms.

The number and percentage of patients who received restricted medications in each treatment group for each treatment period will be summarized by

- ATC Level 4 term and preferred terms for concomitant medications.

- SOC and preferred terms for medical history and adverse event

A patient who reported the same event more than once will be counted only once in the applicable category, SOC (or ATC Level 4), and preferred term for that event.

All restricted medications and surgical procedures will be presented in a by-subject listing.

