**Table 9.1      Restricted Medications and Therapies**

Medication/Therapy	Restricted Dose or Time Period
Orbital irradiation, orbital decompression or strabismus surgery	Any history or planned irradiation or surgery during the trial.
Steroids	Steroids (intravenous or oral) and steroid eye drops within 3 weeks prior to Screening. Systemic steroid use (intravenous or oral) and steroid eye drops are not to be initiated during the trial; however, topical and inhaled steroids are allowed. Steroids for the treatment of infusion reaction are allowed.
Non-steroid eye drops	Non-steroid drops, such as saline or methylcellulose, antihistamines and vasoconstrictors are allowed but must not be used on the day of a clinic visit.
Rituximab (Rituxan® or MabThera®)	Within 12 months prior to the first infusion of trial drug and during the trial.
Tocilizumab (Actemra® or Roactemra®)	Within 6 months prior to the first infusion of trial drug and during the trial.
TEPEZZA	Any previous treatment with TEPEZZA or teprotumumab, including, but not limited to enrollment in this trial or participation in a prior TEPEZZA trial or program.
Monoclonal antibody	Within 3 months prior to Screening.
Non-steroid immunosuppressive agent (other than rituximab or tocilizumab)	Within 3 months prior to the first infusion of trial drug and during the trial.
Investigational agent	Within 60 days or 5 half-lives, whichever is longer prior to Screening or anticipated use during the trial.
Neonatal Fc receptor (FcRn) agents	During the trial.
Illicit drug/alcohol use	History of abuse within the past 2 years or abuse during the trial.

It is recommended to avoid ototoxic medications and medications that may cause muscle spasm/cramps during the trial.

All concomitant treatment (for TED and other conditions) must be documented in the eCRF.

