#### 9.5.3.3 Medical History

Medical history, including tobacco, alcohol and other substance use history and thyroid disease history and treatment, will be captured at Screening. The initial diagnosis of TED must be  $\geq 2$  years but  $<10$  years prior to Screening for trial enrollment. Stable, chronic (inactive) TED must be determined by medical records indicating a CAS  $\leq 1$  in both eyes for at least 1 year prior to Screening or no progression in proptosis, no progression of diplopia (in those with a history of diplopia due to TED) and no new TED symptoms for at least 1 year prior to Screening.

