9.1 Intercurrent Event Handling Strategy for Estimands

Potential intercurrent events (ICEs) like discontinuing from the treatment may occur. Patients who discontinue from the treatment will be encouraged to stay in the trial after those ICEs and data will be collected through the planned study completion visit.

In general, treatment policy strategy will be used to account for the ICEs for defining estimands corresponding to continuous efficacy endpoints, including the primary efficacy endpoint. All efficacy analyses will be based on the observed data except for categorical efficacy endpoints. For categorical endpoints, composite strategy will be used. For binary responder endpoints, patients whose Week 24 assessment is missing will be considered treatment failures (non-responders). For ordinal response endpoint, missing value at Week 24 will be imputed using the last assessment value available for patients whose Week 24 assessment is missing.

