9.2.5 Exploratory Analysis

9.3 Other Efficacy Endpoints

Inferential testing on other efficacy endpoints will be made only when the primary efficacy endpoint reaches statistical significance at 0.05 (two-sided) in favor of TEPEZZA. Other efficacy endpoints (with the main analyses defined in the study eye as appropriate) will be analyzed using the ITT analysis set in a hierarchical manner presented in the order in Section 5.6. For each outcome measure, TEPEZZA will be tested against placebo at the two-sided 0.05 significance level only if the test statistic was statistically significantly in favor of TEPEZZA for the outcome measure preceding it in the hierarchical order.

9.3.1 Proptosis Responder Rate at Week 24

The proptosis responder rate is defined as the percentage of patients with a ≥ 2 -mm reduction from Baseline in proptosis in the study eye, without deterioration [≥ 2 -mm increase] of proptosis in the fellow eye at each scheduled visit.

Population	ITT Analysis Set defined as all patients who were randomized in the trial
Endpoint	
Proportion of patients who have achieved the proptosis response rate at Week 24.
 
The proptosis responder rate at Week 24 is defined as the percentage of patients with a ≥ 2-mm reduction from Baseline in proptosis in the study eye, without deterioration (≥ 2-mm increase) of proptosis in the fellow eye at Week 24.

ICE	Discontinued from treatment early
Population-level Summary	Difference (TEPEZZA minus placebo) in proptosis responder rates at Week 24 between the treatment groups

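### SAP 8.3 cannot count orbital procedures done during the trial, and the visible responder rule counts a proptosis reduction after study-eye decompression or irradiation as response

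*SAP*

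**What the plan says.** **Reporting.** Protocol Table 9.1 gives the restriction on orbital irradiation, decompression and strabismus surgery as "Any history or planned irradiation or surgery during the trial". SAP 8.3 refers to that table and says of the surgical category: "This category will be captured via medical history eCRF form". Protocol 9.5.3.3 says that medical history, including "thyroid disease history and treatment, will be captured at Screening". The schedule of assessments adds a Day 1 entry and no later one.

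The planned table is described as follows: "The number and percentage of patients who received restricted surgical procedures in each treatment group will be summarized by SOC and preferred terms". For medications, the same section writes: "The number and percentage of patients who received restricted medications in each treatment group for each treatment period will be summarized by". So the medication table is split by treatment period and the surgical table is not.

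Procedures done on trial are covered in SAP 8.2: "All concomitant procedures performed during the trial will be presented in a by-subject listing for all patients enrolled". SAP 6.2 tabulates major deviations by arm, treatment period and category. One category is Prohibited Action.

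**Efficacy.** SAP 9.1 applies treatment policy in general to continuous endpoints and a composite strategy to categorical ones. The only failure rule it states for responders is "For binary responder endpoints, patients whose Week 24 assessment is missing will be considered treatment failures (non-responders"). The estimand table in SAP 9.3.1 lists one intercurrent event: "Discontinued from treatment early". The table for the primary endpoint in SAP 9.2 lists the same one.

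**The concern.** Two gaps meet here.

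First, the table that should show a reader how many patients in each arm had an orbital procedure is fed by a form completed before dosing. It will show pre-trial history. The procedures that could alter the Week 24 measurement are those done after Day 1, and these are not in it.

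Second, decompression or irradiation of the study eye is a competing intervention on proptosis. The protocol treats it that way at entry: exclusion criterion 4 bars patients who have had either in the study eye. Yet a patient who has one on trial and attends Week 24 with a reduction of at least 2 mm meets the responder definition, provided the fellow eye has not deteriorated. The observed-case repeat in SAP 9.3.1.1 would count the same patient in the same way.

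The responder rate is first in the testing hierarchy of SAP 5.6, ahead of GO-QoL. With 38 and 19 patients, one misclassified patient can decide that test and whether formal testing continues.

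**Working it through.** **Which forms feed which output**

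| Item (SAP 8.3 unless stated) | Source | Can it include an event after Day 1? |
|---|---|---|
| Restricted medications | Concomitant medications form | Yes, and split by period |
| Illicit drug or alcohol abuse | Medical history and adverse event forms | Yes |
| Restricted surgery or irradiation | Medical history form only | No |
| On-trial procedures (SAP 8.2) | Form not named | Yes, but listed only |

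Only the surgical category has a source that ends before treatment.

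**Design figure.** Inputs from protocol 9.6.7 and SAP 5.1: 38 and 19 patients, difference 2.0 mm, SD 2.5 mm, two-sided 0.05.

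- SE = 2.5 × √(1/19 + 1/38) = 0.702 mm.
- Normal-approximation power = Φ(2.0/0.702 − 1.96) = 81.3%; noncentral t with 55 df gives 79.9%. The stated 81% is reproduced, and no design figure is in question.

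**Effect of one patient.** The documents give no surgical effect size and no frequency. Assumptions: a procedure adds 3 to 6 mm of study-eye reduction at Week 24, the SD is unchanged, all patients have Week 24 data, and the model mean behaves like the arm mean.

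| One case in | Shift in arm mean | Share of 2.0 mm | Responder rate |
|---|---|---|---|
| Placebo (n = 19) | 3/19 = 0.16 to 6/19 = 0.32 mm | 8% to 16% | 1/19 = 5.3 points |
| TEPEZZA (n = 38) | 3/38 = 0.08 to 6/38 = 0.16 mm | 4% to 8% | 1/38 = 2.6 points |

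The responder shift applies to a patient who would otherwise have been a non-responder. A placebo case reduces the observed difference to 1.84 or 1.68 mm, and normal-approximation power falls to about 75% or 67%. A TEPEZZA case moves the difference the other way, by half as much because of the 2:1 allocation.

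**Effect on the Fisher test.** The counts are illustrative.

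| TEPEZZA | Placebo | Two-sided p |
|---|---|---|
| 15/38 | 2/19 | 0.032 |
| 15/38 | 3/19 | 0.081 |
| 14/38 | 2/19 | 0.059 |

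Starting from the first row, one extra placebo responder or one fewer TEPEZZA responder takes the result across 0.05.

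**The case against.** A reader might infer that on-trial procedures vanish from the report. They do not. SAP 8.2 lists them by subject, protocol 9.7 requires deviations to be documented, and SAP 6.2 would count the patient under Prohibited Action if the event is classed as major. That count does not name the procedure or the eye.

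A reader might also infer that the primary analysis is wrong. The documents do not support that. Treatment policy is a declared choice for continuous endpoints, and using the observed value after any event is what it means. The per-protocol set (SAP 5.3.3) can drop such patients, and SAP 9.2.3 repeats the primary model on it. The sensitivity sections, 9.2.2 and 9.3.1.2, are redacted and cannot be judged. But SAP 9.2.3 specifies the per-protocol repeat for the primary endpoint only, so the responder endpoint has no such cover in the readable text.

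The Table 9.1 row can be read as an entry restriction: it speaks of planned surgery, and protocol 9.4.9.2 introduces it in terms of eligibility. On that reading SAP 8.3 does not contradict the protocol. The reporting gap remains, because a procedure not planned at entry can still occur.

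On frequency, inclusion criterion 7 excludes patients needing immediate surgery or planning it, disease must be stable, and non-responders who complete the masked period are offered open-label TEPEZZA. Cases before Week 24 should be few. That they would fall mainly on placebo is an inference; if they did, the bias would run against TEPEZZA, so the gap cannot be presented as favouring the drug.

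**Conclusion.** The point holds as a limited one. As written, the by-arm table in SAP 8.3 cannot count an on-trial orbital procedure, and the readable responder rule credits a reduction of at least 2 mm after study-eye decompression or irradiation to the randomised arm. These are separate issues: changing the form in 8.3 would alter no efficacy result.

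The likely size is small. It rests on an assumed 0 to 2 cases and an assumed 3 to 6 mm effect, neither of which is in the documents. The change is still worth making because the responder test is sensitive to a single patient and gates what follows. It cannot be said that the plan already commits to non-response here: SAP 9.1 names the composite strategy but spells out missing Week 24 data only.

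**What to change.** - **SAP 8.3:** take on-trial orbital irradiation, decompression and strabismus surgery from the concomitant-procedures data. Tabulate them by arm, treatment period and eye, and show pre-trial history separately.
- **SAP 9.1 and 9.3.1:** name on-trial study-eye decompression or irradiation as an intercurrent event, and count the patient as a non-responder at later visits. This extends the composite strategy to a new event and should be described as such.
- **SAP 9.2:** keep the treatment-policy MMRM as the primary analysis. If the redacted sensitivity analyses do not already cover it, add one run with study-eye values after the procedure set to missing.

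The cost is SAP wording, one table and at most one extra model run, on data already collected. The wording should be fixed before unmasking. The downside is that a responder count may fall by a patient, in either arm.

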8.4 Study Treatments

8.4.1 Extent of Exposure

Extent of exposure will be measured and summarized by duration of exposure and total number of infusions and presented by treatment period (double-masked treatment period/open-label treatment period) and TEPEZZA.

The duration of exposure (days) for each treatment period will be calculated as:

The duration of exposure (days) for each treatment period = the last dosing date in each treatment period - the first dosing date in each treatment period +1.

The duration of exposure (days) to TEPEZZA will be calculated as the sum of treatment duration to TEPEZZA in double-masked treatment period and open-label treatment period.

The total number of infusions given is the sum of actual infusions received by patient for each treatment period.

The total number of infusions to TEPEZZA is the sum of TEPEZZA infusions received in double-masked treatment period and open-label treatment period

8.4.2 Treatment Compliance and Modifications

All doses of study drug will be administered and recorded by study site personnel, and any deviations from the dosing schedule will be entered into the patient's eCRF. The study drug administration records will be listed for each patient with study drug administered, start date and time, stop date and time, dose, if there's any dose interruptions incompleteness and reasons.

Summaries will be provided for the count and percentages of patients with each of the following by treatment group for each treatment period:

- Planned doses that were not administered completely
- Infusion interruptions

Planned TEPEZZA doses that were not administered completely and infusion interruptions to TEPEZZA in double-masked treatment period and open-label treatment period will be summarized by treatment group.

9. Efficacy Analysis

Efficacy analysis will be conducted for the double-masked period (as the primary analysis) and open-label period (as the follow-up analysis) separately based on the ITT analysis set. Efficacy analysis results from the primary analysis (i.e., based on the data collected during the double-masked period) will be used for comparison between the two treatment groups. Both study and fellow eyes will be used for the efficacy analyses during the primary analysis, but the statistical inference will be made based on study eye analysis results only. For the follow-up analysis, which will be conducted using subsequent assessments collected during the open-label treatment period, only descriptive summaries of efficacy analysis results will be provided.

